### 9.4 *Statistical methods to be employed*

#### 9.4.1 **General Considerations**

All continuous study assessments will be summarized by treatment and time point (as applicable) using descriptive statistics (n, mean, median, standard deviation, minimum, and maximum). All categorical study assessments will be summarized by treatment and time point (as applicable) using frequency counts and percentages.

Hypothesis testing, unless otherwise indicated, will be performed at a two-sided 0.05 significance level. Where applicable, two-sided 95% confidence intervals will be reported. All p-values will be displayed to four decimal places, with p-values less than 0.0001 presented as '<0.0001' and p-values greater than 0.9999 presented as '>0.9999'. Difference between Articaïne Sterile Topical Ophthalmic Solution (AG-920) and Proparacaine will be calculated as Articaïne Sterile Topical Ophthalmic Solution – Proparacaine, with the 95% CI of the difference being reported for the reference of the treatment therapeutical equivalence.

All study data will be listed by treatment, subject, time point, and eye (as applicable).

Statistical methods will be more fully described in a separate document (Statistical Analysis Plan).

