### 9.4.6 Analysis of Efficacy

Analyses will be performed primarily on the ITT population and will be repeated on the PP population to determine robustness of results. For the primary efficacy endpoint of the proportion of subjects in whom there was adequate local anesthetic effect to perform an eye exam for which the subject is seeing the ophthalmologist, a Pearson chi-square test will be used for the comparison of the two proportions from the two treatment groups. In addition, a two-sided 95% confidence interval for the difference in response rates between the two treatment groups will be calculated. If the difference in response rates is around zero and the *P* value is NOT statistically significant (i.e.,  $P > 0.05$ ), then the therapeutical equivalence of AG-920 to the Proparacaine will be claimed, without reference to a pre-defined non-inferiority margin. The 95% CI of the difference in response rates will be reported to measure the extend or margin of the efficacy equivalence of AG920 to Proparacaine.

Sub-group analyses based upon pre-study characteristics such as sex, iris color, age, and race may be completed to further investigate the efficacy and safety measures.

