### 2.9.1 Primary efficacy analysis

The primary efficacy endpoint for this study is the proportion of subjects with anesthetic effect that is adequate for eye exam as assessed by the PI at 2-4 minutes post application of the dose. The definition of the primary efficacy endpoint is given in [Section 2.6.1](#). The non-parametric Cochran-Mantel-Haenszel (CMH) test with adjustment for study eye side will be used to examine the difference and/or therapeutic equivalence in proportion of subjects with anesthetic effect at 2-4 minutes post dose between the active treatment group and active-control group.

In primary efficacy analysis, rather than to reject the null hypothesis when there is a difference ( $P \leq 0.05$ ) between AG-920 and active-control treatments, this study is designed to accept the null hypothesis that there is no difference in anesthetic effect between AG-920 and active-control treatments ( $P > 0.05$ ), indicating the therapeutic equivalence of AG-920 to Proparacaine without reference to a pre-defined non-inferiority margin.

To further measure the therapeutical equivalence of anesthetic effect of AG-920 to the active-control treatment, between-group difference and its 95% confidence interval (CI) as well as its 90% CI in the proportion of subjects with anesthetic effect (yes=1) vs. non-effect (no=0) will be calculated using a two-way analysis of variance (ANOVA) model with treatment (the effect of interest) and study eye side as the effects. The study-eye-side effect is used as a blocking factor in the model to control the potential treatment differences among the study eye sides. The conventional 90% CI of the between-group difference will be used to measure the extent of the equivalent margin or non-inferiority margin of anesthetic effect of AG-920 to Proparacaine. The conventional rule of the 90% CI of the between-group difference lying

within +/-20% of the reference treatment will be employed to claim the therapeutic equivalence or non-inferiority of AG-920 to Proparacaine.

The primary efficacy analysis will be performed for the ITT population, which will include all randomized subjects who received the complete application of one study dose (i.e., two drops). The analysis model adjusts for the effect of the study eye side. The study-eye-side by treatment interaction will be examined through the summary descriptive statistics of subjects with anesthetic effect for each study eye side.

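### The SAP's +/-20% equivalence margin has no stated scale: it can mean 20 percentage points or 20% of the observed Proparacaine rate, and the second is a stricter, data-dependent limit

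*SAP*

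**What the plan says.** SAP 2.9.1 plans to estimate the "between-group difference and its 95% confidence interval (CI) as well as its 90% CI in the proportion of subjects with anesthetic effect", with success coded 1 and failure 0, from a "two-way analysis of variance (ANOVA) model with treatment (the effect of interest) and study eye side as the effects". Protocol 9.4.1 gives the direction: the difference "will be calculated as Articaïne Sterile Topical Ophthalmic Solution – Proparacaine".

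The SAP then sets its decision limit. It begins "The conventional rule of the 90% CI of the between-group difference lying" and continues "within +/-20% of the reference treatment will be employed to claim the therapeutic equivalence or non-inferiority of AG-920 to Proparacaine". No formula or worked bound follows.

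The same SAP section has a second route to the claim. A CMH result with P > 0.05 is read as "indicating the therapeutic equivalence of AG-920 to Proparacaine without reference to a pre-defined non-inferiority margin". Protocol 9.4.6 has only a rule of that kind: if the difference is near zero and P > 0.05, "then the therapeutical equivalence of AG-920 to the Proparacaine will be claimed, without reference to a pre-defined non-inferiority margin". Protocol 9.1 and 9.2 also say that no margin is pre-defined. The protocol contains no 20% limit.

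**The concern.** The CI is for a difference between two proportions, so it is in percentage points. The limit is worded as a share of the reference treatment. Two readings are open:

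- **Points:** the limits are -20 and +20 percentage points whatever the data show.
- **Relative:** the limits are plus and minus 0.20 times the Proparacaine rate, so 16 points at 80%, 18 at 90% and 19 at 95%.

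The wording leans to the second reading; the quantity being tested leans to the first. On the relative reading, the SAP does not say whether the reference rate is observed, model-adjusted or fixed in advance. If it is the observed rate, the margin is a random quantity known only at the end of the trial, and a CI for the simple difference takes no account of its error. Calling the rule conventional does not settle the scale. Protocol 9.2 says that the sample size was not derived from a margin, so the intended value cannot be worked back from it.

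At stake is whether one and the same result meets the margin rule.

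**Working it through.** **Inputs.** About 30 evaluable subjects per arm (Protocol Summary), with 35 per arm if all 70 are evaluable. Two-sided 90% CI from the treatment plus eye-side model (SAP 2.9.1). The visible documents state no response rate, so 80% to 99%, equal in both arms, is an assumption. There is no planned figure to reproduce.

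**Formula.** With n per arm, the CI is d ± t(0.95, 2n - 3) × sqrt(MSE × 2/n). With failures spread evenly over the two eyes, MSE = [n p1(1 - p1) + n p2(1 - p2)] / (2n - 3). For n = 30, t(0.95, 57) = 1.672.

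**Worked case, 24/30 in each arm.** MSE = 60 × 0.16 / 57 = 0.1684. SE = sqrt(0.1684 × 2/30) = 0.1060. Half-width = 1.672 × 0.1060 = 0.177. The relative margin is 0.20 × 24/30 = 0.160.

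| AG-920 vs Proparacaine | 90% CI (points) | Relative margin | Points reading | Relative reading |
|---|---|---|---|---|
| 24/30 vs 24/30 | -17.7 to +17.7 | 16.0 | claim | no claim |
| 26/30 vs 28/30 | -19.9 to +6.5 | 18.7 | claim | no claim |
| 25/30 vs 26/30 | -19.1 to +12.5 | 17.3 | claim | no claim |
| 27/30 vs 27/30 | -13.3 to +13.3 | 18.0 | claim | claim |
| 29/30 vs 29/30 | -8.0 to +8.0 | 19.3 | claim | claim |

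**Direction.** A rate cannot exceed 100%, so 0.20 × rate is at most 20 points. The relative limits always lie inside the points limits or coincide with them.

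**How often the readings differ.** Both binomials were enumerated exactly, with the ANOVA CI and the eye-side sum of squares taken as zero.

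| True rate, both arms | Equivalence claimed, n = 30: points / relative | Readings differ, n = 30 | Readings differ, n = 35 | Differ on lower limit only, n = 30 |
|---|---|---|---|---|
| 80% | 20.6% / 7.3% | 13.3% | 24.9% | 12.8% |
| 85% | 39.3% / 21.2% | 18.1% | 25.0% | 9.1% |
| 90% | 66.4% / 49.3% | 17.1% | 14.1% | 6.1% |
| 95% | 92.0% / 86.3% | 5.7% | 2.8% | 1.2% |
| 99% | 100.0% / 99.7% | 0.2% | 0.0% | 0.0% |

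**Sensitivity to the interval.** Over every split of failures by eye (15 right, 15 left per arm), 26/30 vs 28/30 and 25/30 vs 26/30 stay discordant. For 24/30 vs 24/30, extreme eye imbalance narrows the CI to ±15.3, which passes both limits. Newcombe and score intervals are discordant for 24/30 vs 24/30 and 25/30 vs 26/30. For 26/30 vs 28/30 their lower limits (-20.7 and -21.6) fail both.

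**Error in a relative margin.** Suppose each arm's proportion has the same variance v. The simple difference has variance 2v. The contrast that carries the reference error is p(AG-920) - 0.8 × p(Proparacaine) at the lower bound, with variance (1 + 0.64)v = 1.64v, and p(AG-920) - 1.2 × p(Proparacaine) at the upper bound, with variance (1 + 1.44)v = 2.44v. Relative to the simple difference the SEs are sqrt(0.82) = 0.91 and sqrt(1.22) = 1.10. Treating the observed margin as fixed is therefore too strict at the lower bound and too lenient at the upper.

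**The case against.** The strongest reply is that the 20% rule is not the only route to a claim. P > 0.05 claims equivalence in Protocol 9.4.6 and again in SAP 2.9.1, and Protocol 9.1 accepts the null hypothesis on the same basis. The SAP introduces the CI as a further measure. In the enumeration at rates of 80-99%, every outcome on which the readings differ has an unstratified Pearson P above 0.05; for 24/30 vs 24/30 the difference is zero. A reader might infer that the scale by itself decides whether equivalence is claimed. The documents do not support that, because the two rules are unranked. But the P > 0.05 rule does not cure the margin either, since the SAP says that the 20% rule will be used to make the claim.

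Other points stand in part:

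- Rates may be high. Protocol section 1 calls surface anesthesia with Proparacaine excellent, and Protocol 4.1 requires children judged able to undergo the exam. Near 99% the readings almost always agree.
- The stricter reading only withholds a claim; it does not show inferiority or a difference.
- A reader might infer that someone will choose the scale after seeing results. Masking covers only subjects and guardians (Protocol 3.5), but the documents do not say when the rule is programmed, and SAP 3.1 finalizes the ITT set before treatment assignment is merged.
- Part of SAP 2.5 is redacted, and the table shells are not included. Either might state a rate or a scale. The decision rule in 2.9.1 should still be complete as written.

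**Conclusion.** The point holds. The plan's only numeric equivalence margin has two possible values, one of them data-dependent and mismatched to the planned CI. Under the assumptions above (equal true rates, 30 per arm, ANOVA CI), the choice matters in roughly one trial in six to eight at true rates of 80-90%, and rarely once nearly all children respond. On the lower limit alone it matters less often at rates of 85% and above. The size depends on a response rate that the visible documents do not give and, for individual results, on the CI method. The conclusion concerns whether the margin rule is met. What the plan finally claims also depends on how the P > 0.05 rule is ranked against it.

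**What to change.** In SAP 2.9.1, before any data are reviewed:

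1. State the limit as a fixed margin on the difference scale. For example: equivalence if the 90% CI for AG-920 minus Proparacaine lies within -20 to +20 percentage points; non-inferiority if its lower limit is above -20 points.
2. If a relative margin is meant, analyze p(AG-920) - 0.8 × p(Proparacaine), with its lower confidence limit above zero. For equivalence also require p(AG-920) - 1.2 × p(Proparacaine) to have its upper limit below zero. Each contrast needs its own CI.
3. Say that this margin rule, not P > 0.05, governs the claim, and whether one bound or both apply.

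Protocol 9.1, 9.2 and 9.4.6 have no matching sentence to edit. They disclaim a pre-defined margin and must be reconciled with the SAP. The cost is a short SAP edit and a protocol amendment of a few sentences under Protocol 12.4. No new data are needed.

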## 2.9 Statistical Methods

Unless specified otherwise, SAS® Version 9.0 or higher will be utilized to perform the statistical analyses of efficacy and safety measures.

Categorical variables will be summarized in general using frequencies and percentages, whereas continuous variables will be summarized in general using descriptive statistics of number of observations (n), mean, standard deviation (SD), minimum (Min), median, and maximum (Max).

In both data listings and CRF domain data tabulations, subject ID will consist of site number plus the subject screening number in the format of XXX-YYY, where XXX denotes the site number and YYY the subject's screening number within the site.

Hypothesis testing, unless otherwise indicated, will be performed at the 5% significance level. All p-values will be rounded to four decimal places; p-values less than 0.0001 will be presented as '<0.0001' in all tables. All group comparisons from analysis of variance (ANOVA) and/or analysis of covariance (ANCOVA) models will be based on Type III sums of squares. In the case of substantial non-normality, results from non-parametric tests will also be reported. All confidence intervals (CI) will be two-sided with 95% coverage, unless stated otherwise.

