Prior to the determination of the primary efficacy variable, handling of missing values that occur prior to eye exam is described in [Section 2.8](#).

The primary efficacy endpoint will also be analyzed for the PP population as well as for subgroups of the ITT population, such as male vs. female, Caucasian vs. Non-Caucasian, age groups, and iris color dark brown vs. other colors.

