## 4.5 Efficacy Results and Tabulations

### 4.5.1 Results of primary efficacy analysis

Descriptive and inferential statistics on the ITT population of the proportion of subjects with anesthetic effect assessed by the PI at 2 to 4 minutes post dose will be presented in [Table 2.1.1](#).

For the PP population, the results of the same proportion analysis on the number of subjects with anesthetic effect at 2 to 4 minutes post dose will be presented in [Table 2.1.2](#).

The by-site summary of descriptive statistics of the number of subjects with anesthetic effect at 2 to 4 minutes post dose will be presented in [Table 2.1.3](#).

The results of the proportion analysis on the number of subjects with anesthetic effect at 2 to 4 minutes post dose will be presented for the sub-populations of boys vs. girls in [Tables 2.2.1](#) and [2.2.2](#); for 8 years or younger vs. 9 years or older in [Tables 2.2.3](#) and [2.2.4](#); for Caucasian vs. Non-Caucasian in [Tables 2.2.5](#) and [2.2.6](#); and for iris color dark brown vs. other colors in [Tables 2.2.7](#) and [2.2.8](#).

Individual subjects' primary efficacy data (i.e., anesthetic effect) assessed post dose on Day 1 by Investigator, with and without imputation, will be listed by treatment for the ITT population ([Listing 6](#)).

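### The SAP repeats the primary analysis inside eight subgroups at the 5% level and plans no treatment-by-subgroup contrast, so it risks false within-subgroup differences and cannot show whether the effect varies.

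*SAP*

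**What the plan says.** - **Protocol 9.4.6** treats subgroup work as optional: such analyses "may be completed to further investigate the efficacy and safety measures". SAP 4.1 is also permissive, saying that sub-population datasets *may* be defined.
- **SAP 2.9.1** is firmer: "The primary efficacy endpoint will also be analyzed for the PP population as well as for subgroups of the ITT population". It names sex, race, age and iris colour as examples.
- **SAP 4.5.1** assigns the results to numbered tables. They "will be presented for the sub-populations of boys vs. girls" in Tables 2.2.1 and 2.2.2, with age (8 or younger, 9 or older), race and iris colour following through Table 2.2.8.
- **SAP section 7** gives all eight the same summary-and-analysis title form as primary Table 2.1.1. By-site Table 2.1.3 is titled as a summary only, and 4.5.1 describes it as descriptive.
- **SAP 2.9** sets the level: "Hypothesis testing, unless otherwise indicated, will be performed at the 5% significance level". Protocol 9.4.1 makes it two-sided. Nothing sets a different level for subgroups.
- **SAP 2.9.1** has two equivalence rules for the primary analysis. One reads P > 0.05 as "indicating the therapeutic equivalence of AG-920 to Proparacaine without reference to a pre-defined non-inferiority margin". The other requires the 90% CI of the difference to lie within +/-20% of the reference.
- The only interaction mentioned is treatment by study-eye side, and it is handled descriptively. Neither document labels the subgroup tables exploratory, orders them or adjusts for their number.

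**The concern.** Eight separate tests of the same endpoint give eight chances of a spurious P <= 0.05, and the plan does not say how such a result would be read. The tests also answer the wrong question. A significant result in boys and a non-significant one in girls does not show that the drugs compare differently in boys and girls; that needs the difference between the two differences, which is not planned. The opposite error is possible too. The analysis being repeated includes a rule that takes non-significance as equivalence, and that rule gets easier to meet as the table gets smaller. At stake are statements about sex, age, race or iris colour drawn from a trial of 60 to 70 children.

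**Working it through.** **Inputs from the documents.** About 70 randomized and at least 60 evaluable (Protocol 9.2); 1:1 allocation; eight subgroups as four complementary pairs (SAP 4.5.1); CMH test stratified by study-eye side (SAP 2.9.1); two-sided 5%. The sample size was set by regulatory direction, so there is no power figure to reproduce, and the documents state no subgroup error rate.

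**Assumptions.** Response 50% to 98%, equal in both arms under the null; subgroup shares from 50/50 to 80/20; the four factors independent of each other.

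**1. Upper reference for eight tests.** If independent: 1 - 0.95^8 = 0.337. The subgroups overlap across factors, so the true rate is lower.

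**2. Simulation of the SAP's own test.** CMH by eye side in each of eight subgroups, 20,000 trials per scenario, N = 60 and 70, three sets of shares, no true difference. Chance of at least one P <= 0.05:

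| True response | Range over N and shares |
|---|---|
| 50% | 24.8-26.0% |
| 70% | 24.5-25.6% |
| 80% | 22.4-25.2% |
| 90% | 15.8-18.5% |
| 95% | 7.2-8.9% |
| 98% | 1.7-2.3% |

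The fall at high response comes from discreteness. The per-test rate is about 4.7-4.9% at 70% response, but 1.1-1.5% at 95% and 0.2-0.3% at 98%.

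**3. If the P > 0.05 rule were carried into a subgroup.** Exact enumeration of the Pearson chi-square test (the Protocol 9.4.6 test), true response 90% vs 70%:

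| Per arm | P > 0.05 |
|---|---|
| 10 | 86% |
| 15 | 72% |
| 30 (whole trial, N = 60) | 50% |
| 35 (whole trial, N = 70) | 44% |

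The CMH test gives similar subgroup figures: 85% at 20 children in total and 73% at 30. The last two rows show that the rule already fails often in the whole trial; subgroups make it worse.

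**4. The 90% CI rule at the same sizes.** Two-way ANOVA interval, +/-20 read as absolute points:

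| Children in total | Equal 90%: passes | 90% vs 70%: passes |
|---|---|---|
| 60 | 62% | 4.5% |
| 30 | 29% | 1.8% |
| 20 | 12% | 1.0% |
| 12 | 27% | 6.8% |

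Smaller subgroups generally make this rule harder to meet. The rise at 12 occurs because the ANOVA interval has zero width when all responses are alike.

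**5. Precision of the missing contrast.** For N = 60, a 50/50 split (15 per arm in each subgroup) and 90% response, the variance of one subgroup difference is 2 x 0.9 x 0.1 / 15 = 0.012. The difference between two such differences has SE = sqrt(2 x 0.012) = 0.155, so its 95% half-width is 1.96 x 0.155 = 0.30. The interval spans about 30 points either way.

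**The case against.** Several points against the concern carry weight.

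- **A reader might infer that small subgroups will be declared equivalent by default.** The documents do not say so. SAP 2.9.1 introduces the accept-the-null rule for the primary analysis and ties that analysis to the ITT population. For subgroups, the SAP says only that the endpoint is analysed and the results presented. The 90% CI rule, which the SAP says will be used to claim equivalence, usually becomes stricter as subgroups shrink. This objection stands.
- **False equivalence is mainly a fault of the primary analysis.** With 44-50% for the whole trial, the weakness lies in reading non-significance as equivalence. This stands too, and the harm should not be counted twice.
- **The one-in-four figure needs response of 50-80%.** Inclusion criterion 2 requires children judged capable of an eye exam, and Protocol section 1 calls proparacaine's surface anesthesia excellent, so high response is at least as plausible. The figure is a ceiling.
- **The permissive wording suggests an exploratory purpose.** In part. Protocol 9.4.6 and SAP 4.1 say *may*, but SAP 2.9.1 and 4.5.1 say *will*. Optional wording also leaves the interpretation unsettled.
- **The P values are inferred.** The table shells are not in the documents. But the SAP's own contrast between by-site summaries and summary-and-analysis tables makes inferential content the natural reading.

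None of this supplies the missing between-subgroup contrast.

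**Conclusion.** The concern holds in a limited form. The SAP commits to eight subgroup repeats of the primary proportion analysis at 5% each, with no treatment-by-subgroup contrast, so the method cannot show whether the effect varies by sex, age, race or iris colour. With truly equal drugs, at least one false within-subgroup treatment difference arises in about 25% of trials at 50-80% response, 16-18% at 90%, 7-9% at 95% and about 2% at 98%. These figures rest on assumed response rates and subgroup shares.

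They count treatment differences inside a subgroup. A reader might take them as false differences between subgroups, but the plan does not test those. The 72% at 15 per arm is conditional on the P > 0.05 rule being applied in the subgroup tables, which the SAP neither states nor excludes. The primary ITT result is unaffected.

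**What to change.** In SAP 2.9.1, 4.1 and 4.5.1:

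1. Replace the within-subgroup P values in Tables 2.2.1 to 2.2.8 with the response rate per arm and the difference with its 95% CI. The analysis being repeated already yields a 95% CI, but the ANOVA interval collapses when all children in a subgroup respond alike, so name an interval method that does not.
2. For each of the four factors, add the difference between the two subgroup differences with its 95% CI. Report these as estimates, not tests: four further independent tests at 5% would carry a family-wise rate of 1 - 0.95^4 = 18.5%.
3. State that these tables are exploratory and that neither equivalence rule of 2.9.1 applies to them.
4. Use the same verb (*may* or *will*) for subgroup analyses throughout the SAP, and reconcile it with Protocol 9.4.6.

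The cost is SAP wording and four contrasts from data already collected, with no extra children or procedures. The downside is that no subgroup claims can be made, and the contrast intervals will be wide (about +/-30 points in the example above).
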